4.2 Pre-Treatment Criteria

4.2.1 Cycle 1, Day 1

If screening laboratory assessments were completed \leq 72 hours prior to cycle 1 day 1, laboratory tests do not need to be repeated on cycle 1 day 1 and the screening laboratory values can be used as the cycle 1 day 1 values. If cycle 1 day 1 laboratories are performed, the values do not need to re-meet eligibility criteria, participants will be allowed to initiate treatment at the treating investigator's discretion.

4.2.2 Subsequent Cycles

Management guidelines for toxicities associated with study treatment are located in **Section 6**.

4.3 Agent Administration

4.3.1 Acalabrutinib

Acalabrutinib administration instructions:

- Acalabrutinib should be administered orally twice daily, approximately every 12 hours.
- If a dose is missed, it can be taken up to 3 hours after the scheduled time with a return to the normal schedule with the next dose. If it has been > 3 hours, the dose should not be taken and the participant should take the next dose at the scheduled time.
- The tablets should be swallowed intact with water. Participants should not attempt to open, crush, chew, or dissolve the tablets.
- Acalabrutinib can be taken with or without food.
- If the participant vomits following a dose, the dose should not be re-taken. Instead, the participant should proceed with their next scheduled dose as clinically appropriate.
- Order of administration of the study agents does not matter.

4.3.2 Umbralisib

Umbralisib administration instructions:

- Umbralisib should be administered orally once daily, approximately every 24 hours.
- If a dose is missed, it can be taken up to 12 hours after the scheduled time with a return to the normal schedule with the next dose. If it has been > 12 hours, the dose should not be taken and the participant should take the next dose at the scheduled time.
- The tablets should be swallowed intact. Participants should not attempt to crush, chew, or dissolve the tablets.
- Umbralisib should be taken within 30 minutes of a meal.
- If the participant vomits following a dose, the dose should not be re-taken. Instead, the participant should proceed with their next scheduled dose as clinically appropriate.
- See **Section 4.4** for information regarding required anti-viral and anti-PJP prophylaxis.
- Order of administration of the study agents does not matter.

4.3.3 Ublituximab

Ublituximab administration instructions:

- Ublituximab will be administered as an intravenous (IV) infusion through a dedicated infusion line.
- Medication and resuscitation equipment must be available per institutional guidelines prior to ublituximab administration for the emergency management of potential anaphylactic reactions. See hypersensitivity and infusion reaction guidance below.
- Ublituximab should not be administered as an IV push or bolus.
- Diluted ublituximab should be checked before administration for cloudiness, color, or deposits. Ublituximab should not be administered if it does not conform to the specifications.

- It is recommended that ublituximab be administered immediately after dilution. It should NOT be mixed the day before and mixing should only occur once confirmed that the patient is eligible for therapy on the day of treatment.
- Ublituximab should not be mixed with other medicinal products.
- Ublituximab should only be diluted in 0.9% NaCl before use.
- Participants must be pre-medicated with an antihistamine (diphenhydramine 25-50 mg or equivalent) and a corticosteroid (dexamethasone 10 – 20 mg or equivalent). Decision of using oral or IV pre-medication is at the treating investigator's discretion except for cycle 1 days 1 and 2, when IV pre-medication and diphenhydramine 50 mg are required:
 - If oral pre-medication: start the ublituximab infusion 45 – 60 minutes after the ingestion of the oral pre-medications.
 - If IV pre-medication: start the ublituximab infusion 30 minutes (+ 5 minute window) after the completion of the last pre-medication infusion.
 - Adjusting antihistamine and corticosteroid doses, adjusting the timing of administration and/or additional pre-medications may be used at investigator discretion for additional prophylaxis against infusion related reactions.
 - Administration of oral acetaminophen 650 mg (or equivalent) may be as clinically warranted, or in participants who experience fever/pyrexia after the first infusion.
- Infusion-related hypotension may occur, investigators should consider holding anti-hypertensive medications 12 – 24 hours prior to and throughout the infusion. Decision to withhold anti-hypertensive medication is at the treating investigator's discretion.
- For patients at risk for tumor lysis syndrome in the opinion of the treating investigator, prophylaxis with allopurinol or similar per recommended institutional standards should be considered.
- Order of administration of the study agents does not matter.
- Ublituximab should be administered at the dose, rate, and schedule indicated in the tables below.

Table 5: Ublituximab Infusion Rate Cycle 7 Days 1 and 2

Cycle 7	Ublituximab Dose	Total Volume to be Infused	Infusion Rate ¹			
			Start – 30 min	30 min – 1 hr	1 hr – 2 hrs	2 hrs – 4 hrs
Day 1	150 mg	250 mL	10 mL/hr	20 mL/hr	35 mL/hr	100 mL/hr
Day 2	750 mg	500 mL	10 mL/hr	20 mL/hr	85 mL/hr	200 mL/hr

1: A ± 2 minute window is allowable for adjustment of the infusion rate.

Table 6: Ublituximab Infusion Rate Cycle 7 Days 8 and 15					
Cycle 7	Ublituximab Dose	Total Volume to be Infused	Infusion Rate¹		
			Start – 1 hr	1 hr – 2 hrs	2 hrs – 3 hrs
Day 8, 15	900 mg	500 mL	50 mL/hr	150 mL/hr	300 mL/hr

1: A ± 2 minute window is allowable for adjustment of the infusion rate.

Table 7: Ublituximab Infusion Rate Cycles 8 – 12 Day 1					
Cycle Day	Ublituximab Dose	Total Volume to be Infused	Infusion Rate¹		
			Start – 30 min	30 min – 90 min	
1	900 mg	500 mL	200 mL/hr	400 mL/hr	

1: A ± 2 minute window is allowable for adjustment of the infusion rate.

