4. TREATMENT PLAN

4.1 Treatment Regimen

A treatment cycle is defined as 28 consecutive days. Treatment will be administered on an outpatient basis. Reported adverse events and potential risks are described in **Section 7**. Appropriate dose modifications are described in **Section 6**.

Participants will receive acalabrutinib at the FDA approved dose of 100 mg by mouth twice daily and umbralisib at 800 mg by mouth once daily continuously throughout each treatment cycle. Ublituximab will be given IV starting with cycle 7 on days 1, 2, 8, and 15 and cycles 8-12 on day 1.

Participants who are in bone marrow and CT confirmed CR at the end of cycle 12 will stop dosing with acalabrutinib and umbralisib.. Participants not in CR will continue to cycles 13-24.

Participants will have peripheral blood monitoring for MRD as described in the **Study Calendar** in **Section 10**. If early relapse or recurrence is detected, the patient will undergo restaging with a CT scan and a bone marrow biopsy / aspirate. At the discretion of the treating investigator, patients with early relapse not meeting iwCLL criteria for retreatment may resume dosing with acalabrutinib and umbralisib until further disease progression, unacceptable toxicity, or other criteria are met as described in **Section 5.5**. The study agents will be resumed at the dose levels the participant was receiving prior to discontinuation. Dosing will resume for a maximum of 12 additional treatment cycles, such that participants may receive a maximum total of 36 cycles of study therapy.

Table 4: Regimen Description

Agent	Premedications; Precautions	Dose	Route	Schedule ¹	Cycle Length
Acalabrutinib	May be taken with or without food.	100 mg	By mouth	Twice Daily	
Umbralisib	Take within 30 minutes of a meal. Participants are required to receive prophylactic anti-viral and anti-pneumocystis jiroveci pneumonia (PJP) treatment, refer to Section 5.4 .	800 mg	By mouth	Once Daily	28 days

Table 4: Regimen Description

Agent	Premedications; Precautions	Dose	Route	Schedule ¹	Cycle Length

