Ublituximab	
Pre-medicate with an antihistamine (diphenhydramine 50 mg or equivalent) and a corticosteroid (dexamethasone 10 – 20 mg or methylprednisolone 80 mg or equivalent).^{2,3,4}
 
 • If oral pre-medication: start the ublituximab infusion 45 – 60 minutes after the ingestion of the oral pre-medications • If IV pre-medication: start the ublituximab infusion 30 – 35 minutes after the completion of the last pre-medication infusion 	See Section 5.3.3	IV	
Cycle 7: Days 1, 2, 8, 15
 
Cycles 8 – 12: Day 1
	

 1. Order of administration of the study agents does not matter. 2. Diphenhydramine must be 50 mg IV on Cycle 7 day 1 and 2, but may be reduced to 25 mg on subsequent infusions in the absence of infusion related reactions and at treating physician discretion. After the completion of cycle 8, use of corticosteroid pre-medication may be discontinued with approval from the sponsor-investigator if the participant has not experienced any infusion-related or hypersensitivity reactions. 3. Administration of oral acetaminophen 650 mg (or equivalent) may be as clinically warranted, or in participants who experience fever/pyrexia after the first infusion. 4. Infusion-related hypotension may occur, investigators should consider holding anti-hypertensive medications 12-24 hours prior to and throughout the infusion. Decision to withhold anti-hypertensive medication is at the treating investigator's discretion. 					

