7.3.7 Preparation

Ublituximab should not be mixed with other medicinal products. Ublituximab should only be diluted in 0.9% NaCl before use. No data are available for other solutions such as 5% dextrose and 5% mannitol.

Ublituximab is available in 150 mg (6 mL quantity vial) or 900mg (36 mL quantity vial) single use vials as a 25 mg/mL concentrate for dilution. Dilutions for ublituximab are as indicated in the tables below.

Ublituximab preparation instructions for 900mg Single use vial C7D1 & C7D2

- Withdraw appropriate volume of ublituximab from the vial as per table
- For day 1 infusion, dilute 6 mL ublituximab into a 250 mL 0.9% sodium chloride infusion bag for administration on day 1. If not used immediately, diluted solutions must be refrigerated. After allowing the diluted bag to come to room temperature, use immediately.
- For day 2 infusion, dilute the remaining 30 mL into a 500 mL 0.9% sodium chloride infusion bag at the same time, and store at 2-8°C (36-46°F) for up to 24 hours for use on Day 2. After allowing the diluted bag to come to room temperature, use immediately.
- Label each infusion bag clearly.
 - Day 1 = 150 mg bag

- Day 2 = 750 mg bag
- Mix diluted solution by gentle inversion prior to use. Do not shake or freeze.

Table 17: Ublituximab Dilutions for Cycle 7 Day 1 & Day 2

Dose of ublituximab for infusion	Volume of ublituximab (25 mg/mL)	Volume of NaCl 0.9% to be removed	Final volume in perfusion bag
Day 1: 150 mg	6 mL	6 mL	250 mL
Day 2: 750 mg	30 mL	30 mL	500 mL

Table 18: Ublituximab Dilutions for Cycle 7 Day 8 & Beyond

Dose of ublituximab for infusion	Volume of ublituximab (25 mg/mL)	Volume of NaCl 0.9% to be removed	Final volume in perfusion bag
900 mg	36 mL	36 mL	500 mL

Diluted ublituximab should be checked before administration for cloudiness, color, or deposits. Ublituximab should not be administered if does not conform to the specifications. Immediately inform TG Therapeutics, Inc. at [contact] with any product quality concerns or questions.

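### Do the misdated premedication rule and the two mixing instructions for the Cycle 7 Day 2 ublituximab bag call for a change to the plan?

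*Combined protocol and SAP*

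**What the plan says.** On premedication, Section 4.3.3 requires an antihistamine and a corticosteroid before each infusion. It lets the investigator choose oral or IV "except for cycle 1 days 1 and 2, when IV pre-medication and diphenhydramine 50 mg are required". Section 4.1 gives the schedule: "Ublituximab will be given IV starting with cycle 7 on days 1, 2, 8, and 15". Table 4 footnote 2, in the same section, states: "Diphenhydramine must be 50 mg IV on Cycle 7 day 1 and 2". The infusion-rate table for the split first dose, which sits inside Section 4.3.3, is headed "Table 5: Ublituximab Infusion Rate Cycle 7 Days 1 and 2".

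On mixing, Section 4.3.3 says of ublituximab: "It should NOT be mixed the day before and mixing should only occur once confirmed that the patient is eligible for therapy", with that confirmation made on the day of treatment. Section 7.3.7 contains a step list headed "Ublituximab preparation instructions for 900mg Single use vial C7D1 & C7D2". Its Day 2 step reads: "For day 2 infusion, dilute the remaining 30 mL into a 500 mL 0.9% sodium chloride infusion bag at the same time". The bag is then refrigerated "for up to 24 hours for use on Day 2". Section 7.3.3 separately allows diluted product to be kept refrigerated for up to 24 hours.

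**The concern.** Read literally, the only mandatory-IV rule in Section 4.3.3 applies on days when no ublituximab is given. A site using that section alone would find route and diphenhydramine dose (25 to 50 mg) open at the two infusions for which the rule was evidently written. The two texts also differ in scope. Section 4.3.3 speaks of IV premedication as a whole, whereas footnote 2 fixes the IV route for diphenhydramine only. Correcting the cycle number would therefore still leave the corticosteroid route unsettled.

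The mixing instructions look worse. A pharmacy using the 900 mg vial cannot obey both sections: the Day 2 bag is either made on Day 1 or it is not. The stakes would be site conduct at the infusions where reactions are most likely, and uncertainty over which behaviour counts as a protocol departure. Nothing in the concern touches type I error, power or sample size.

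**Working it through.** The plan gives no figure to reproduce on this point, so the check is a comparison of texts with some simple counts.

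**Step 1: premedication texts side by side.**

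| Source | Days named | What is fixed |
|---|---|---|
| Section 4.3.3, premedication bullet | Cycle 1, days 1 and 2 | IV route for premedication; diphenhydramine 50 mg |
| Section 4.1, Table 4 footnote 2 | Cycle 7, days 1 and 2 | Diphenhydramine 50 mg IV |
| Section 4.1, regimen text | First ublituximab in cycle 7 | Schedule |
| Section 4.3.3, Table 5 | Cycle 7, days 1 and 2 | 150 mg then 750 mg |

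A site that follows footnote 2 breaks neither text, because the Section 4.3.3 exception covers no infusion and its general rule permits the IV route and 50 mg. The texts are compatible in practice. What footnote 2 does not supply is the corticosteroid route at those two infusions.

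**Step 2: mixing texts, with the vial arithmetic.** The concentration is 25 mg/mL (Section 7.3.2).

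- Day 1 bag: 6 mL × 25 mg/mL = 150 mg.
- Day 2 bag: 30 mL × 25 mg/mL = 750 mg.
- Together: 36 mL × 25 mg/mL = 900 mg, exactly one 900 mg single-use vial.

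So the Section 7.3.7 steps use one vial in one session, and the Day 2 bag is necessarily mixed the day before its infusion. Section 4.3.3 forbids that. Section 7.3.3 governs how long diluted product may be stored, not when mixing may occur, so it does not settle the matter. With 150 mg vials the conflict does not arise: Day 1 needs one vial and Day 2 needs 750 / 150 = 5, and each bag can be made on its own day.

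**Step 3: how many infusions.**

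- Scheduled per participant: 4 in cycle 7 (days 1, 2, 8, 15) + 5 in cycles 8 to 12 (day 1) = 9.
- Premedication wording: 2 of 9 = 22%; ceiling 60 × 2 = 120 infusions.
- Mixing conflict: 1 of 9 = 11%; ceiling 60 × 1 = 60 infusions, and only where the 900 mg vial was used.

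The ceilings assume that all 60 planned participants enrolled and reached cycle 7. The documents give neither that number nor vial use.

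**Step 4: does either point reach a result?** Section 12.6.2 makes everyone with at least one dose of at least one study agent evaluable for the primary endpoint. The premedication route and the day a bag was mixed do not enter that definition. Section 12.4 declares efficacy at 10 or more complete remissions in Cohort 1 and 13 or more in Cohort 2, and neither cut-off uses these inputs. The safety trigger in Section 12.3 counts qualifying toxicities in the first triple-therapy cycle without reference to how a bag was prepared or how premedication was given.

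**Step 5: does either point reach future conduct?** Section 5.5 records that, as of March 2023, umbralisib and ublituximab are no longer supplied, and that participants still on treatment may continue acalabrutinib. The instructions in question therefore have little or no remaining use.

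**The case for a change.** The best case for acting is that these instructions govern the highest-risk infusions and cost only wording to repair. Section 2.3.3 reports infusion reactions in 75% of patients in one single-agent study, with Grade 3 reactions in 33%. In another it reports them in 40%, mostly on the first infusion day, although none there was grade 3 or higher. Grade 4 or higher infusion reactions in the first triple-therapy cycle count towards the consultation trigger in Section 12.3. Appendix C, Section 3.7.1, requires all departures from the protocol to be reported to the sponsor and the IRB of record. For a Day 2 bag made from a 900 mg vial, the protocol does not say which conduct was the departure, and no section is ranked above the other.

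Part of this stands. The mixing contradiction is real, and only the sponsor can say which instruction governed. The corticosteroid route at the first two infusions is also open.

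The safety argument is weaker than it looks. A bag mixed on Day 1 need not be infused on Day 2. The toxicity holds in Section 5.3 apply whether or not a bag exists, and Section 4.3.3 calls for inspection of the diluted product before use. If Day 2 treatment is held, the consequence the documents support is an unused bag, not an unsafe dose. On deviations, no infusion has been shown whose classification was in doubt.

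**Conclusion.** Both observations are accurate, but neither calls for a change to the plan. The premedication point is a clerical slip in the cycle number, with the diphenhydramine rule correctly dated in Table 4 footnote 2 and a narrow gap on the corticosteroid route. The mixing point is a true contradiction limited to one vial size and one of nine infusions.

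The ceilings are 120 and 60 infusions, assuming full enrolment, everyone reaching cycle 7 and, for the second, use of the 900 mg vial throughout. No effect on the complete remission endpoint, its decision rules or the analysis population is shown. This rests on Section 5.5 meaning what it says: with ublituximab no longer supplied, new wording would steer little or no future practice.

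The passages must still be reconciled by the sponsor in the trial record, so that past infusions can be classified consistently. Which instruction governed is the sponsor's decision.

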4.3.4 Infusion-Related Reaction Guidelines – Ublituximab

Infusion-related reactions (including severe reactions) have been reported with ublituximab administration. Guidelines are provided for patients who experience such reactions.

Symptomatic infusion reactions may be treated at the discretion of the treating investigator and as per institutional standards of practice, including but not limited to: oral acetaminophen 650 mg (or equivalent), corticosteroids, antihistamines, oxygen, and bronchodilators.

If an infusion-related reaction is observed at any time during the ublituximab treatment, the treating investigator may reduce the infusion flow rate at their discretion.

The following are recommended infusion rate reduction/delay guidelines for patients who experience severe Infusion-Related Reactions (IRR's) that result in treatment interruption. Final decision for infusion rate reduction/delay or discontinuation resides with the treating investigator.

If grade 4 anaphylaxis is observed at any point during ublituximab treatment, permanently discontinue ublituximab treatment and intervene as per treating investigator discretion and institutional standards of practice.

1st or 2nd Infusion Interruption (same day):

- Hold infusion and closely monitor patient, institute symptomatic medical management until resolution of IRR symptoms.
- Following the judgment of the treating investigator, and provided the patient is stable, the infusion may be resumed at no more than half the previous rate.
- If the patient does not experience any further IRR symptoms, infusion rate escalation may resume at the increments and intervals as appropriate for the treatment cycle dose.

3rd Infusion Interruption (same day):

- Discontinue infusion for that day – monitor patient for resolution of all symptoms. Patient should have all vital signs completed as well as any other standard of care procedures completed as warranted by the treating investigator prior to release of patient from study site.
- Any remaining diluted investigational product should be discarded.

If an ublituximab infusion is discontinued, the next scheduled dose should be administered according to the protocol dosing schedule.

4.4 General Concomitant Medication and Supportive Care Guidelines

No investigational or commercial agents or therapies other than acalabrutinib, umbralisib, or ublituximab may be administered with the intent to treat the participant's malignancy.

Investigators should use appropriate supportive medications to address toxicities that arise during the study, including but not limited to anti-emetics, anti-diarrheals, hematopoietic growth factors and blood product transfusion.

4.4.1 Umbralisib Prophylactic Anti-Viral Treatment

Participants receiving umbralisib are required to start prophylactic treatment with anti-PJP and anti-viral therapy prior to day 1 of treatment. Choice of PJP and anti-viral prophylaxis is per investigator discretion and institutional standard of care, with the following as recommendations:

- Anti-viral Prophylaxis: Valtrex 500 mg daily or Acyclovir 400 mg BID or equivalent.
- PJP Prophylaxis: Sulfamethoxazole/trimethoprim 800 mg / 160 mg three times per week, or 400 mg / 80 mg daily, or if allergic, atovaquone 750 mg twice daily. Dapsone 100 mg daily may also be used if other agents are contraindicated or unavailable but is not recommended. If dapsone is used, be aware that methemoglobinemia is not uncommon in CLL patients treated with dapsone.
- Final choice of PJP and anti-viral prophylactic therapy is per treating investigator discretion.

Participants should continue prophylactic treatment for at least one year after stopping protocol therapy.

If anti-viral or anti-bacterial prophylaxis is not tolerated, alternate to a different prophylactic agent, reduce the dose or modify the schedule for the prophylactic agent, or discontinue prophylaxis at the treating investigator's discretion.

4.4.2 Hepatitis B Monitoring and Anti-Viral Prophylaxis

All participants are required to have testing for hepatitis B surface antigen (HBsAg) and

hepatitis B core (HBc) antibody at screening. If HBc antibody is positive, the subject must also be evaluated for the presence of hepatitis B viral (HBV) DNA by PCR (see **Appendix B**). Subjects with positive HBc antibody and negative HBV DNA by PCR are eligible, but serial monitoring of HBV DNA is required monthly.

Subjects with a prior history of hepatitis must be closely monitored as clinically indicated based on liver tests and any observed signs/symptoms such as jaundice, abdominal pain, dyspepsia, dark-colored urine often accompanied by lighter-than-normal colored stools, nausea, vomiting or fatigue.

For patients with a prior history of hepatitis B who experience an increase in liver enzymes while on study, hold ublituximab immediately and assess for active hepatitis B infection. If negative for hepatitis B by viral load testing, ublituximab may be resumed. If reactivation of hepatitis B is confirmed, institute hepatitis B antiviral treatment. Ublituximab may be resumed at investigator discretion once hepatitis B infection has resolved, with continued monitoring as described above.

Serious or life-threatening reactivation of viral hepatitis may occur in subjects treated with acalabrutinib or ublituximab. Use of anti-viral prophylaxis will be permitted at the treating investigator's discretion. Entecavir is the preferred agent for pharmacologic prophylaxis. Use of an agent other than entecavir must be discussed with the sponsor-investigator. HBV DNA should be monitored every 1-2 months while a patient is receiving pharmacologic prophylaxis. If the HBV DNA level becomes detectable, all study medications must be discontinued and infectious disease consultation should be obtained. If a patient completes study therapy while taking entecavir, they should remain on entecavir for at least one year after completion of all therapy. If discontinuation of entecavir is considered, patients should have their LFTs and HBV DNA level monitored weekly for the first two months.

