2.8.20 Participants with evidence of chronic active Hepatitis B (HBV, not including patients with prior hepatitis B vaccination or positive serum Hepatitis B antibody), chronic active Hepatitis C infection (HCV), active cytomegalovirus (CMV), or known history of human immunodeficiency virus (HIV):

- If HBc antibody is positive or the patient has a known history of hepatitis B, the subject must be evaluated for the presence of HBV DNA by PCR (see **Appendix B**). Subjects with a known history of hepatitis B and a positive HBc antibody but a negative HBV DNA by PCR are eligible if on suppressive therapy. Subjects with no known history of hepatitis B, with positive HBc antibody and negative HBV DNA by PCR, are eligible but serial monitoring of HBV DNA by PCR is required, see **Section 5.4**. Subjects with positive HBV DNA by PCR are not eligible.
- Participants with positive HBsAg are to be excluded.
- If HCV antibody is positive, the subject must be evaluated for the presence of HCV RNA by PCR. Subjects with positive HCV antibody and negative HCV RNA by PCR are eligible. Subjects with positive HCV RNA by PCR are not eligible.
- If the subject is CMV IgG or CMV IgM positive, the subject must be evaluated for the presence of CMV DNA by PCR. Subjects who are CMV IgG or CMV IgM positive but who are CMV DNA negative by PCR are eligible, anti-viral prophylaxis should be considered per treating investigator discretion.

2.8.21 History of allergic reactions attributed to study drugs including active product or excipients, or compounds of similar chemical or biologic composition to acalabrutinib, umbralisib, or ublituximab, including participants with a history of anaphylaxis (excluding infusion-related reactions) in association with previous anti-CD20 administration.

- 2.8.22 Participants requiring concomitant treatment with any medications or substances that are strong inhibitors or inducers of CYP3A4 at the time of study enrollment. Because the lists of these agents are constantly changing, it is important to regularly consult a frequently-updated medical reference. As part of the enrollment/informed consent procedures, the participant will be counseled on the risk of interactions with other agents, and what to do if new medications need to be prescribed or if the participant is considering a new over-the-counter medicine or herbal product.

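### Section 4.4.2 gives two inconsistent responses to hepatitis B reactivation and should state one stop rule that expressly covers acalabrutinib, on or off prophylaxis

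*Combined protocol and SAP*

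**What the plan says.** Four parts of the protocol bear on this point.

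- **Eligibility (2.8.20).** Two groups positive for hepatitis B core (HBc) antibody may enter with undetectable HBV DNA. Participants with known hepatitis B and "a positive HBc antibody but a negative HBV DNA by PCR are eligible if on suppressive therapy". For the second group the condition is monitoring rather than therapy: "Subjects with no known history of hepatitis B, with positive HBc antibody and negative HBV DNA by PCR, are eligible", with serial HBV DNA testing.
- **Section 4.4.2, first paragraph.** "Subjects with positive HBc antibody and negative HBV DNA by PCR are eligible, but serial monitoring of HBV DNA is required monthly". No action on a positive result is given here.
- **Section 4.4.2, third paragraph.** Its scope is "For patients with a prior history of hepatitis B who experience an increase in liver enzymes while on study". Ublituximab is held and active infection is looked for. If reactivation is confirmed, antiviral treatment starts, and then: "Ublituximab may be resumed at investigator discretion once hepatitis B infection has resolved, with continued monitoring as described above". Acalabrutinib is not mentioned.
- **Section 4.4.2, fourth paragraph.** It opens with the hazard: "Serious or life-threatening reactivation of viral hepatitis may occur in subjects treated with acalabrutinib or ublituximab". It leaves prophylaxis to the investigator's discretion, names entecavir as the preferred agent, and continues: "HBV DNA should be monitored every 1-2 months while a patient is receiving pharmacologic prophylaxis". The next sentence is the stop rule: "If the HBV DNA level becomes detectable, all study medications must be discontinued and infectious disease consultation should be obtained". No restart clause follows.

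Section 5.5 records that umbralisib and ublituximab have no longer been provided since March 2023, while participants still on treatment may continue acalabrutinib.

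**The concern.** The two paragraphs describe the same clinical event, reactivation of hepatitis B on study, and prescribe different responses. One holds a single drug and foresees its return. The other stops every study drug. A site that finds the third paragraph first, because enzymes have risen in a participant with prior hepatitis B, could follow it to the end without meeting any instruction on acalabrutinib.

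The protocol treats the hazard as grave. Section 2.4.1.2 reports HBV reactivation in the acalabrutinib programme, with liver failure and death in one case. Acalabrutinib is also the only agent that participants may now continue. At stake are participant safety and uniform conduct across sites. The primary analysis, the sample size and the error rates are untouched.

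**Working it through.** No arithmetic applies; the check compares the provisions and asks whether any reading makes them agree.

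| Provision | Who and when | Ublituximab | Acalabrutinib | Restart |
|---|---|---|---|---|
| 4.4.2, paragraph 1 | HBc antibody positive, HBV DNA negative; monthly test | no action stated | no action stated | not stated |
| 4.4.2, paragraph 3 | prior hepatitis B, enzyme rise | held | silent | ublituximab, at investigator discretion |
| 4.4.2, paragraph 4 | HBV DNA detectable | discontinued | discontinued | not stated |

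**Reading A: the stop rule covers everyone tested.** This is the plain reading. The sentence carries no limit of its own, and its paragraph opens with all subjects on acalabrutinib or ublituximab. Acalabrutinib then stops in every participant with detectable DNA. But any participant with prior hepatitis B whose reactivation shows as detectable DNA falls under both paragraphs, and these differ on which drugs stop and on whether ublituximab may return.

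**Reading B: the stop rule covers only participants on prophylaxis.** The position of the sentence permits this. A participant with positive HBc antibody and no known history may be off prophylaxis, since 2.8.20 sets no therapy condition for this group and 4.4.2 makes prophylaxis discretionary. The mandatory monthly test then has no stated consequence for acalabrutinib. The third paragraph does not fill the gap: it needs a prior history and an enzyme rise, and it names only ublituximab.

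**Reading C: as A, but the stop is temporary.** The third paragraph can then follow in sequence and supply the restart rule for ublituximab. Acalabrutinib has no restart rule.

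Each reading leaves something unreconciled. Other sections do not settle it:

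- **Section 5.1 (Dose Delays)** holds all agents when attribution is unknown or shared, with a limit of 28 days for acalabrutinib that can be extended by agreement with the sponsor-investigator. It does not mention hepatitis B and prescribes a hold, not a discontinuation.
- **Table 12, liver rows**, do not refer to 4.4.2. Grade 1 and a first Grade 2 event keep all three agents at current dose, whereas the third paragraph of 4.4.2 holds ublituximab on an enzyme rise in a participant with prior hepatitis B. Grade 3 or higher holds all three agents, then restarts acalabrutinib first, at full dose, once liver tests recover, with no condition on HBV DNA.
- **Table 12 footnotes** require a check for viral hepatitis before steroids but give no action on a positive result. They allow acalabrutinib management to follow the prescribing information, which is permissive.
- **Section 4.5** lists general off-therapy criteria and does not name hepatitis B.
- **Section 4.4.1** requires antiviral prophylaxis with umbralisib and suggests valacyclovir or acyclovir. This is separate from the discretionary, entecavir-based prophylaxis of 4.4.2, so it does not place everyone on the latter.

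**The case against.** The strongest reply is that the stop rule means what it says. Its wording has no qualifier, it is the only stated action for the monthly DNA test, and limiting it to participants on prophylaxis adds words and leaves that test pointless. This largely stands. A reader might infer that the protocol fails to settle acalabrutinib for every participant off prophylaxis. The documents do not support that: the gap appears only if a site adopts the narrower reading. Moreover, participants with known hepatitis B and positive HBc antibody enter only on suppressive therapy, so the exposed group is mainly those with no known history.

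A reader might also infer a flat contradiction on ublituximab. That needs the stop to be permanent, and the protocol does not say so. Section 4.3.4 speaks of a discontinued infusion followed by the next scheduled dose, Section 4.1 resumes agents at the dose taken before discontinuation, and Table 12 adds the word permanently where that is meant. If the stop is temporary, the two paragraphs can be read in order. The difference in which drugs are stopped remains.

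Nor does the third paragraph authorise continuing acalabrutinib; it is silent. The general safeguards (the Grade 3 hold, the all-agent hold in 5.1, investigator judgment in 4.5) protect participants with severe liver toxicity. They do not address a positive DNA test with normal or mildly raised enzymes.

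Finally, ublituximab was scheduled only for cycles 7 to 12 and is no longer supplied, so its part of the inconsistency is largely historical.

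**Conclusion.** The inconsistency is real but limited. Section 4.4.2 gives two responses to reactivation, only one of which addresses acalabrutinib, and no other section reconciles them. The live part is acalabrutinib: a site following the third paragraph alone, or reading the stop rule as confined to participants on prophylaxis, could continue it with detectable HBV DNA while another site stops it.

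The number exposed cannot be derived. The documents do not report how many participants are HBc-antibody-positive, how many of those are off prophylaxis, or how many remained on acalabrutinib after March 2023. It is probably small and may be zero; no probability is claimed. The conclusion assumes that some HBc-antibody-positive participants are off hepatitis B prophylaxis, which the eligibility text and the discretionary wording allow but do not establish. The absence of a word on permanence is missing detail for the sponsor to supply, not a separate error.

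The correction is worth making because the event is serious and the change is cheap.

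**What to change.** Replace the stop sentence in the fourth paragraph of 4.4.2 with one rule: *Whenever HBV DNA becomes detectable or reactivation is confirmed, on or off prophylaxis, stop all study medications still being given, including acalabrutinib, start or change antiviral treatment, and obtain infectious disease consultation.*

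Make the third paragraph's response to confirmed reactivation refer to that rule, and replace its ublituximab restart clause with a statement that any restart of any agent requires sponsor-investigator agreement. Add a pointer to 4.4.2 in the liver rows of Table 12.

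The cost is a wording amendment and a cross-reference. The downside is that a few participants with detectable HBV DNA off prophylaxis would stop acalabrutinib who might otherwise have continued.
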